- Study safety is evaluated continuously by representatives of BMS WWPS, who operate independently from the clinical team and monitor safety across all BMS protocols. AEs are monitored continuously by WWPS. Signal detection is performed at least monthly and ad hoc throughout the study by the SMT and composed, at a minimum, of the WWPS medical safety assessment physician (Chair of the SMT) and WWPS single-case review physician, the study Sponsor/Medical Monitor (or designee), the study biostatistician, pharmacovigilance scientist, and the epidemiologist. The SMT monitors actual or potential issues related to participant safety that could result in a significant change in the medical benefit-risk balance associated with the use of study intervention. Furthermore, investigators will be kept updated of important safety information during teleconferences between investigators and the BMS clinical team, which will be held on a regularly scheduled basis. If appropriate, select safety issues may be escalated to a senior-level, multidisciplinary, BMS-wide Medical Review Group for further evaluation and action. To support safety oversight, BMS has established an ongoing processes for collection, review, analysis, and submission of individual AE reports and their aggregate analyses.
- The SMT will review the totality of the safety data available throughout the study. Safety data will be continuously monitored and will be informed by a Bayesian framework (see [Section 10.5.1](#)). After considering overall safety and if an excessive number of pre-specified safety events are observed, an ad hoc data review by the DMC will be considered as needed.

The minutes of these meetings will be documented in the Trial Master File. The SMT will not share responsibilities with the DMC. Decisions on safety, toxicity, and benefit-risk will be solely the responsibility of BMS and will take account of the totality of the data available and in consideration of any DMC recommendations (see [Section 3.3](#) for additional details).

5.1.5 *Blinded Independent Radiology Central Review*

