10.5 Interim Analyses

10.5.1 Safety Continuous Monitoring

A Bayesian continuous monitoring framework will be utilized to monitor for toxicity for a safety-evaluation period of 12 weeks of treatment and detect safety signals that may lead to changes in study conduct.⁴² In addition to the study DMC, a SMT consisting of BMS research and development representatives (including clinical development, drug safety and statistics) and external representatives (including selected investigators) will regularly meet to evaluate the

accumulating unblinded safety data of participants of the study. If the specified safety boundary (number of AEs) is exceeded in Arm A, the DMC will be contacted for additional evaluations of unblinded data as needed.

For this type of monitoring, the proportion of TRAEs of Grade 3 to Grade 4 is used to provide formal monitoring boundaries. These boundaries were established using a prior distribution of Beta(0.66, 1.37), which is a weak informative prior reflecting the approximate proportion of Grade 3 to Grade 4 TRAEs in the nivolumab plus ipilimumab arm in Study CA209227 (ie, 33%). The posterior distribution at any time point is Beta(0.66 + n, 1.37 + [m-n]), where n is the number of participants observed with Grade 3 to Grade 4 TRAEs, and m is the total number of safety-evaluable participants. (For the definition of safety-evaluable participants, see [Section 10.3](#)).

The monitoring function for toxicity is defined as the posterior probability of (Grade 3 to Grade 4 TRAEs > 40% | cumulating data) > 0.85. This criterion implies that there is a greater than 85% predictive probability that the aggregate toxicity rate in Arm A is larger than 40%. It will be applied after at least 8 randomized participants in Arm A are safety-evaluable and can be performed on a continuous basis afterwards. The resulting boundaries are presented in Table 10.5.1-1. This monitoring boundary criterion is not binding.

If, anytime during the study (first 126 participants), this Grade 3 to Grade 4 TRAE proportion reaches the pre-specified threshold for toxicity, then, taking into account all available safety information, additional evaluation will be conducted to allow a complete by treatment arm safety assessment and risk benefit evaluation.

Table 10.5.1-1: Safety Continuous Monitoring Boundary for Arm A

Number of Safety-evaluable Participants in Arm A ^a	Toxicity Boundary (# Evaluable Participants with Event) for > 85 Probability of TRAE > 40%
8	5
9-10	6

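### Section 10.5.1 gives its toxicity trigger as both exceeding and reaching the boundary, and neither reading of the printed table matches the stated 0.85 posterior criterion at all sizes

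*Combined protocol and SAP*

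**What the plan says.** Section 10.5.1 sets up Bayesian monitoring of Grade 3 to 4 TRAEs in Arm A, starting once 8 Arm A participants are safety-evaluable. The prior is Beta(0.66, 1.37). In the posterior, "n is the number of participants observed with Grade 3 to Grade 4 TRAEs" and m is the number of safety-evaluable participants. The criterion is "the posterior probability of (Grade 3 to Grade 4 TRAEs > 40% | cumulating data) > 0.85". Table 10.5.1-1 lists the resulting boundaries for 8 to 60 participants, under the column header "Toxicity Boundary (# Evaluable Participants with Event) for > 85 Probability of TRAE > 40" (per cent). A footnote says thresholds above 60 will be calculated, with no upper limit. The section states that the criterion is not binding.

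Two sentences turn the boundary into action:

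- "If the specified safety boundary (number of AEs) is exceeded in Arm A, the DMC will be contacted", which continues that the contact is for additional evaluation of unblinded data as needed.
- "If, anytime during the study (first 126 participants), this Grade 3 to Grade 4 TRAE proportion reaches the pre-specified threshold for toxicity", after which a by-arm safety and benefit-risk evaluation is to be conducted.

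Section 5.1.4 adds that "The SMT will review the totality of the safety data available throughout the study" and that, after an excess of pre-specified events, "an ad hoc data review by the DMC will be considered as needed".

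**The concern.** One table serves two actions, and the two sentences need different counts from it. At the first look one fires at 5 of 8 and the other at 6 of 8. The first sentence also describes the boundary as a number of AEs, whereas the posterior and the table header count participants. The second sentence says the rule applies at any time, then limits it to 126 participants without naming an arm.

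This is the trial's only formal quantitative toxicity rule. Non-binding status governs what follows a crossing. It does not settle whether a crossing has occurred, and the people applying the rule need one answer to that.

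**Working it through.** **Inputs.** Prior, posterior, 40% limit, 0.85 cut-off, first look at 8 and printed boundaries: Section 10.5.1 and Table 10.5.1-1. Total 180 randomized 2:1: Section 5.2, so Arm A is 180 × 2/3 = 120. The true event rates used below are illustrative; 33% is the plan's own reference rate for nivolumab plus ipilimumab.

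**Step 1: reproduce the table.** For n participants with an event among m evaluable, compute Pr(rate > 0.40) under Beta(0.66 + n, 1.37 + m − n). The boundary is the smallest n for which this is above 0.85.

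| n of m | Posterior | Pr(rate > 0.40) | Printed boundary |
|---|---|---|---|
| 5 of 8 | Beta(5.66, 4.37) | 0.853 | 5 |
| 6 of 8 | Beta(6.66, 3.37) | 0.957 | |
| 19 of 40 | Beta(19.66, 22.37) | 0.810 | 19 |
| 20 of 40 | Beta(20.66, 21.37) | 0.883 | |
| 26 of 57 | Beta(26.66, 32.37) | 0.786 | 26 |
| 27 of 57 | Beta(27.66, 31.37) | 0.855 | |
| 28 of 60 | Beta(28.66, 33.37) | 0.836 | 28 |
| 29 of 60 | Beta(29.66, 32.37) | 0.892 | |

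There are 60 − 8 + 1 = 53 tabulated sizes. The printed entry is the smallest qualifying count at 29 of them, including every size from 8 to 18. At the other 24 (m = 19, 21, 28, 30, 35, 37, 39, 40, 42, 44, 46 to 49 and 51 to 60) it is one participant below what the criterion requires. None of the alternative priors, target rates and cut-offs tried reproduces the whole table.

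**Step 2: compare the two triggers with the criterion.** Where the table is correct (29 sizes), *reaches* matches the criterion and *exceeded* is one participant late. Where the table is one too low (24 sizes), *exceeded* matches and *reaches* is one participant early. Neither word, applied to the printed table, reproduces the stated rule throughout.

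**Step 3: size at the first look.** With X binomial(8, p):

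- p = 0.60: P(X ≥ 5) = 0.594; P(X ≥ 6) = 0.315.
- p = 0.50: P(X ≥ 5) = 0.363; P(X ≥ 6) = 0.145.

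**Step 4: size over repeated looks.** An exact binomial recursion, checking after each evaluable participant from 8 onward, gives the probability of at least one trigger:

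| True rate, by m | *Reaches* printed table | *Exceeded* printed table | Recomputed table, at or above |
|---|---|---|---|
| 50%, by 20 | 0.61 | 0.39 | 0.59 |
| 50%, by 60 | 0.89 | 0.81 | 0.85 |
| 33%, by 60 | 0.18 | 0.08 | 0.165 |

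**Step 5: the span.** The only other use of 126 is in Section 10.5.1.1, where it counts all randomized participants at the efficacy interim analysis (126/180 = 70%). On that reading Arm A contributes 126 × 2/3 = 84, leaving 120 − 84 = 36, and 36/120 = 30%, outside the formal evaluation commitment. This conflicts with the same sentence's statement that the rule applies at any time. If 126 means Arm A, it exceeds the 120 planned for that arm and limits nothing.

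**The case against.** The strongest reply is that little turns on this in practice. The rule is non-binding, and the Sponsor and SMT see unblinded safety data. SMT signal detection is at least monthly. The DMC reviews the first 8 Arm A participants after 6 weeks of treatment and meets periodically thereafter (Section 10.5.1.2 gives at least every 6 months as an example). The loss from *exceeded* also shrinks with time: by 60 participants at a true 60% rate, the two readings trigger with probability 99.6% and 99.0%. All of this stands and limits the consequence. It does not say which count is a crossing.

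A reader might also infer more than the documents support:

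- *Action always comes one event late.* This fails at 24 of 53 sizes, where the printed table is itself too low.
- *Counting AEs delays action.* One participant can have several AEs, so counting them would bring the trigger forward. The formula and table header already fix the unit as participants; the AE wording is simply wrong.
- *Thirty per cent of Arm A goes unmonitored.* The figure needs 126 to count both arms, which Section 10.5.1 does not state, and the table footnote is open-ended. Only the formal commitment would end. Running the rule to 120 rather than 84, using *reaches* on the printed table and the computed 0.85 boundary above 60, raises the trigger probability from 48.9% to 51.9% at a true 40% rate and from 92.5% to 96.3% at 50%.
- *Sections 10.5.1 and 5.1.4 contradict each other on DMC involvement.* Both qualify the DMC's evaluation with as needed, and contacting the DMC is a different act from the DMC conducting a review.
- *The boundary replaces the safety lead-in.* The amendment attributes the lead-in's removal to data from CA020002 and does not call the boundary a substitute.

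**Conclusion.** The concern holds as an inconsistency between the trigger wording, the printed table and the stated criterion. The *exceeded* sentence is one participant late at every size from 8 to 18 and at 29 of 53 sizes overall, which roughly halves or more than halves triggering at the first look for true rates of 60% and 50%. The printed table is one participant too low at the other 24 sizes. The span of 126 either conflicts with the claim that the rule applies at any time or exceeds the arm; the 30% figure depends on the first of those readings.

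The posterior results need only the prior, limit and cut-off in Section 10.5.1. The trigger probabilities assume independent participants, a constant true rate and a check after every evaluable participant. Whether 40% and 0.85 are suitable limits is not judged here. This should be corrected, but it does not leave the trial without safety oversight.

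**What to change.** 1. Recompute Table 10.5.1-1 from the stated Beta(0.66, 1.37) prior and 0.85 cut-off, each entry being the smallest participant count that meets the criterion. This raises 24 entries by one and leaves 29 unchanged. Changing the wording to at or above the printed table without recomputing would fix those 24 errors in place.
2. Reconcile *exceeded* and *reaches* into one trigger, expressed in safety-evaluable Arm A participants with an event and consistent with the criterion. DMC contact and by-arm evaluation can remain separate actions.
3. Delete the parenthesis describing the boundary as a number of AEs.
4. Reconcile the 126-participant limit with the any-time wording and the open-ended table footnote by defining the span by arm.

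The boundary stays non-binding, and no toxicity threshold or clinical action is proposed. The cost is a recalculated table and edits within one section. Relative to the *exceeded* reading, the chance of at least one alert by 60 participants at a true 33% rate rises from about 8% to about 16.5%, each alert costing one DMC contact.

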11-12	7
13-14	8
15-16	9
17-19	10
20-21	11
22-23	12
24-25	13
26-28	14
29-30	15
31-32	16
33-35	17

Table 10.5.1-1: Safety Continuous Monitoring Boundary for Arm A

Number of Safety-evaluable Participants in Arm A ^a	Toxicity Boundary (# Evaluable Participants with Event) for > 85 Probability of TRAE > 40%
36-37	18
38-40	19
41-42	20
43-44	21
45-47	22
48-49	23
50-52	24
53-54	25
55-57	26
58-59	27
60	28

Abbreviation: TRAE, treatment-related adverse event.

^a Additional thresholds for the monitoring of > 60 participants will be calculated by the Statistician.

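### Table 10.5.1-1 does not follow from the rule in Section 10.5.1: at 24 of 53 listed sizes the boundary is one event too low, and the trigger is worded two ways

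*Combined protocol and SAP*

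**What the plan says.** Section 10.5.1 (Safety Continuous Monitoring) gives a complete Bayesian rule for the proportion of Arm A participants with a Grade 3 to 4 TRAE.

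- **Prior:** "These boundaries were established using a prior distribution of Beta(0.66, 1.37"). With n events among m safety-evaluable participants, the posterior is Beta(0.66 + n, 1.37 + m − n).
- **Criterion:** the monitoring function is "defined as the posterior probability of (Grade 3 to Grade 4 TRAEs > 40% | cumulating data) > 0.85". It applies once at least 8 Arm A participants are safety-evaluable.
- **Link to the table:** "The resulting boundaries are presented in Table 10.5.1-1". The table covers m = 8 to 60 in 24 rows, and its column heading repeats the 85% and 40% figures.
- **Trigger for contacting the DMC:** the DMC is contacted "If the specified safety boundary (number of AEs) is exceeded in Arm A".
- **Trigger for further evaluation:** further evaluation follows when "this Grade 3 to Grade 4 TRAE proportion reaches the pre-specified threshold for toxicity". That sentence opens "If, anytime during the study (first 126 participants").
- **Status:** "This monitoring boundary criterion is not binding".
- **Above 60:** the table footnote says "Additional thresholds for the monitoring of > 60 participants will be calculated by the Statistician".

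**The concern.** Prior, target rate and cut-off are all stated, so the table should be reproducible exactly. If it is not, the Safety Management Team (SMT) works from counts that do not match the described criterion, and nobody can tell which of the two was intended.

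The wording of the trigger adds a separate ambiguity. *Reached* means an alert at the listed count; *exceeded* means an alert one event later. Both problems carry over to the thresholds above 60, which have still to be calculated and cannot be consistent with both the printed table and the printed formula.

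**Working it through.** **Inputs, all from Section 10.5.1.** Prior Beta(0.66, 1.37); target rate 0.40; posterior cut-off 0.85; first look at m = 8; listed counts from Table 10.5.1-1 for m = 8 to 60, which is 53 sizes.

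**Formula.** For each m, find the smallest n with

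1 − F(0.40; 0.66 + n, 1.37 + m − n) > 0.85,

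where F is the Beta distribution function, and compare it with the listed count.

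**Step 1: where the table is reproduced.** At m = 8 the posterior is 0.6515 for 4 events and 0.8532 for 5, so the rule gives 5, as listed. Every size from 8 to 18 agrees; at m = 18, 10 events give 0.8826.

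**Step 2: where it is not.** The first failure is m = 19. The listed count of 10 gives 0.8365; the rule needs 11 (0.9231). Further examples:

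| m | Listed count | Posterior at listed count | Count the rule requires |
|---|---|---|---|
| 19 | 10 | 0.8365 | 11 |
| 28 | 14 | 0.8330 | 15 |
| 40 | 19 | 0.8100 | 20 |
| 48 | 23 | 0.8494 | 24 |
| 52 | 24 | 0.7964 | 25 |
| 57 | 26 | 0.7861 | 27 |
| 60 | 28 | 0.8364 | 29 |

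The full list of mismatches is m = 19, 21, 28, 30, 35, 37, 39, 40, 42, 44, 46–49 and 51–60. That is 24 of 53 sizes, in 16 of 24 rows, and 14 of the 24 lie in m = 46–60. The listed count is always one below the rule and never above it. In rows 48–49, 53–54, 55–57, 58–59 and 60, no size meets the criterion.

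**Step 3: can another reading explain the table?**

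- *Rounding the posterior to two decimals* clears only m = 21, 39, 48 and 55, leaving 20 mismatches.
- *A different cut-off with the same prior and target* cannot work. The table flags 26/57 (0.786) but does not flag 9/17 (0.826). Scanning cut-offs from 0.70 to 0.95 in steps of 0.0005, the best values (about 0.80 to 0.82) still miss 8 sizes.
- *Reading the count as one to be exceeded* means alerting at the listed count + 1. That equals the rule at the 24 mismatching sizes, but is one event late at the other 53 − 24 = 29, starting at the first look, where 5/8 already gives 0.8532.
- *A different target at cut-off 0.85* was also tried: 0.385 leaves 5 mismatches and 0.39 leaves 6. Neither value is in the protocol.

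**Step 4: what it does to alerts.** Probability of at least one crossing, by exact recursion over the binomial path with a look after every participant from m = 8:

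| True rate | By m | Table, reached | Stated rule | Table, exceeded |
|---|---|---|---|---|
| 33% | 18 | 13.1% | 13.1% | 4.0% |
| 33% | 40 | 17.2% | 15.7% | 6.7% |
| 33% | 60 | 18.5% | 16.5% | 7.8% |
| 40% | 18 | 28.0% | 28.0% | 11.7% |
| 40% | 40 | 40.9% | 37.2% | 23.6% |
| 40% | 60 | 46.9% | 41.8% | 30.1% |
| 50% | 18 | 57.0% | 57.0% | 34.2% |
| 50% | 40 | 80.7% | 76.6% | 66.8% |
| 50% | 60 | 89.2% | 85.4% | 80.6% |

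**Step 5: the 126.** Section 5.2 plans about 180 participants at 2:1, so Arm A has 180 × 2/3 = 120. A window of 126 exceeds that, so it cannot sensibly count Arm A alone. If it counts both arms, Arm A contributes 126 × 2/3 = 84. Section 10.5.1 does not say which is meant.

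**The case against.** The strongest reply is that little turns on this. The column heading ties the listed count to the 85% criterion, which favours *reached*, and on that reading the table is never late: it alerts at the same count as the rule or one event sooner, the cautious direction. Only 8 of the 33 sizes up to m = 40 differ. The boundary is non-binding, the SMT looks at all the safety data (Section 5.1.4), and the DMC reviews unblinded data on its own schedule (Section 10.5.1.2). The crossing probabilities assume a look after every participant; batched looks would give lower figures. The *exceeded* column rests on the less favoured reading. And the 126 may be explained in material not available here.

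All of that stands as a limit on size, and it is why the effect is called modest. It does not remove the discrepancy. The table is presented as the output of a formula that does not produce it, and no reading tried makes the two agree. The wording matters in its own right: up to m = 18, where table and rule coincide, the choice between *reached* and *exceeded* alone moves the alert probability at a true rate of 50% from 57.0% to 34.2%. The two sentences may describe different actions, but they refer to the same set of counts, so a reader needs to know whether the listed count is itself an alert.

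**Conclusion.** The point holds and should be fixed. At 24 of 53 listed sizes Table 10.5.1-1 is one event below what the stated prior, target and cut-off require, and the trigger is worded inconsistently. This rests only on the parameters printed in Section 10.5.1.

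Read as *reached*, the table raises the crossing probability by m = 60 over the stated rule by 18.5 − 16.5 = 2.0 points at a true rate of 33%, 46.9 − 41.8 = 5.1 points at 40%, and 89.2 − 85.4 = 3.8 points at 50%. Read as *exceeded*, it lowers it by 16.5 − 7.8 = 8.7, 41.8 − 30.1 = 11.7 and 85.4 − 80.6 = 4.8 points. These figures assume independent participants with a constant event rate and continuous looks from m = 8. Which of rule or table was intended cannot be settled from the documents.

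**What to change.** Reconcile rule and table. Which one governs is for the sponsor to decide.

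1. **Either** recompute the table from the stated parameters: 8: 5; 9–10: 6; 11–12: 7; 13–14: 8; 15–16: 9; 17–18: 10; 19–20: 11; 21–23: 12; 24–25: 13; 26–27: 14; 28–29: 15; 30–32: 16; 33–34: 17; 35–36: 18; 37–38: 19; 39–41: 20; 42–43: 21; 44–45: 22; 46–47: 23; 48–50: 24; 51–52: 25; 53–54: 26; 55–57: 27; 58–59: 28; 60: 29. **Or** keep the table and state the prior, target and cut-off that produced it.
2. Use one trigger word in both paragraphs.
3. Say whether the 126 participants are counted across both arms or in Arm A, and whether they are randomized or safety-evaluable.
4. Calculate the thresholds above 60 on the same basis. If the stated rule is kept and the window reaches 84 in Arm A, they are 61: 29; 62–64: 30; 65–66: 31; 67–68: 32; 69–71: 33; 72–73: 34; 74–75: 35; 76–78: 36; 79–80: 37; 81–82: 38; 83–84: 39.

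The cost is one recomputed table or one sentence of parameters, one word and one clarification. The trade-off is that recomputing makes some alerts one event later than the present table read as *reached*, while keeping the table means stating a different rule.

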The clinical studies of BMS-986207 have been designed to minimize the overall risk to participants. In Study CA020002, no DLTs were reported in the 6 DLT-evaluable participants treated with BMS-986207 600 mg Q3W in combination with nivolumab plus ipilimumab; thus, this dose was considered tolerable. In comparison to other anti-TIGIT antibodies in development that have a wild type Fc region, BMS-986207 has an inert Fc region that may provide less toxicity in participants when used as monotherapy or in combination with PD-(L)1 or CTLA-4 inhibitors. To minimize potential risks, a lower dose of ipilimumab 1 mg/kg at a 6-week dosing interval will be used, which is also the same dose and dosing interval used in CheckMate 227. All study interventions will occur at infusion centers with medical monitoring and the capability to manage infusion reactions, including anaphylaxis. Complete blood counts and chemistry (including liver enzyme) tests will be carried out prior to administration of study therapy and on a weekly basis during the first 4 weeks of treatment. In addition, complete physical examinations (PEs) will be conducted on Day 1 of each new cycle, along with weekly symptom-directed targeted PEs during the first 4 weeks of treatment.

Please see [Section 7.4.4](#) for treatment algorithm for infusion reactions and [Section 7.4.1](#) for toxicity management of study intervention.

Nivolumab and ipilimumab combinations have a well-defined toxicity profile based on a safety database of patients treated with the combination across multiple tumor types. Multiple dose administration regimens were evaluated and nivolumab plus low-dose ipilimumab at 1 mg/kg was shown to be safe and tolerable. In CheckMate 227, a TRAE was reported in the majority (76.7%) of participants with 1L NSCLC treated with nivolumab plus ipilimumab while Grade 3 to Grade 4 TRAEs were reported in 32.8% of participants. Moreover, a TRAE leading to discontinuation was reported in 18.1% of participants. A pattern of immune-related adverse events has been defined, for which management algorithms have been developed; these are provided in [Appendix 6](#). Most high-grade events were manageable with the use of corticosteroids or hormone replacement therapy (endocrinopathies) as instructed in these algorithms.

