5.2 Number of Participants

Approximately 180 randomized participants are expected to be randomized in a 2:1 ratio to the 2 treatment arms stratified by PD-L1 expression and histology in pre-specified subgroups.

To ensure the randomized population is representative of the NSCLC population and to allow for appropriate subgroup analyses, total enrollment and/or enrollment in specific PD-L1 subgroups may be adjusted to ensure enrollment of at least 105 randomized participants with tumor cell PD-L1 expression $\geq 1\%$ with at least 75 randomized participants with tumor cell PD-L1 expression 1% - 49%, and at least 75 randomized participants with tumor cell PD-L1 expression $< 1\%$, based on central laboratory results.

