10.2 Sample Size Determination

The sample size of the study is calculated to have a sufficient probability of making the correct decision and have a low probability of making an incorrect decision under the pre-defined go criteria of primary efficacy endpoint of PFS in the PD-L1 $\geq 1\%$ subgroup. Using a Bayesian augmented control (BAC) design, a portion of the control cohort for Study CA020016 will be

borrowed from participants treated with nivolumab plus ipilimumab in Study CheckMate 227 whose baseline prognostic factors are similar to the current randomized population. Based on the results in the CheckMate 227 study, it is assumed that the median PFS in Arm B is 5 months with a constant HR of 0.605 of Arm A vs Arm B for the PD-L1 $\geq 1\%$ subgroup. The pre-defined go criteria at the end of the trial is probability (Pr) (HR < 1) > 0.9 and Pr (HR < 0.7) > 0.5. With the above assumption, 64 PFS events will need to be observed across the 2 arms, and there is 72.2% probability of making a go decision for a scenario at the interim analysis occurring at about 70% of the events, and 78.1% probability of making a go decision at the final analysis. This assumes 12 months for accrual and a minimum of 10 months follow up, for a total of 105 randomized participants with PD-L1 $\geq 1\%$ expression, with approximately 180 participants randomized under current assumptions of prevalence in the primary subgroup. The participants will be randomized to the BMS-986207 with nivolumab plus ipilimumab (Arm A) and the nivolumab plus ipilimumab (Arm B) in a 2:1 ratio.

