10.3 Analysis Sets

For the purposes of analysis, the following populations are defined:

Population	Description
Enrolled	All participants who sign informed consent and are registered in IRT
Treated	All participants who received any amount of study intervention
Randomized	All participants who were randomized using IRT
Randomized PD-L1 \geq 1%	All participants who were randomized using IRT with \geq 1% PD-L1 tumor expression
Safety-evaluable	All randomized participants who have received study intervention (all 3 components) and have completed the safety-evaluation period of 12 weeks, or who discontinued any study intervention due to toxicity prior to completing the safety-evaluation period.
PK	All participants who received at least 1 dose of study intervention and had any available concentration-time data
Immunogenicity	All treated participants who have baseline and at least 1 post-baseline pre-infusion immunogenicity assessment

Abbreviations: IRT, interactive response technology; PD-L1, programmed death-ligand 1; PK, pharmacokinetic.

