10.5.1.2 DMC Analysis

The DMC will have access to periodic unblinded interim reports of safety and efficacy to allow a benefit-risk assessment, based on data summaries as specified in the charter, at pre-planned meetings (eg, at least every 6 months or as specified in the charter). The DMC review will include early monitoring for tolerability of the triplet combination in the first 8 participants who are randomized to Arm A. This analysis will occur after the 8 participants have completed 6 weeks of treatment. Additional and any ad hoc analyses as requested based on emerging safety signals may also be performed to support additional ad hoc DMC meetings (eg, based on assessment of aggregate data by the BMS SMT). Results will not be shared with BMS prior to the final analysis, unless otherwise specified under pre-specified conditions described in the charter. An independent statistician external to BMS will perform the analyses. Details are included in the DMC charter.

The DMC will also conduct an efficacy interim analysis as described in Section 10.5.1.1.

The DMC/Review Board charter will describe the statistical analysis and procedures related to DMC operations.

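### Until 8 Arm A participants are safety-evaluable the protocol gives no numeric aggregate toxicity boundary, and a Grade 3-4 treatment-related event in someone who stays on all drugs is not counted until week 12

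*Combined protocol and SAP*

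**What the plan says.** The numeric monitor in Section 10.5.1 is a Beta posterior for the Grade 3-4 TRAE rate in Arm A. The prior is Beta(0.66, 1.37), and the boundary is crossed when the posterior probability of a rate above 40% exceeds 0.85. On when it starts: "It will be applied after at least 8 randomized participants in Arm A are safety-evaluable". Table 10.5.1-1 begins at 8 participants with a boundary of 5. The boundary is non-binding; crossing it leads to contact with the DMC.

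Section 10.3 defines safety-evaluable participants as those who received all three components and "have completed the safety-evaluation period of 12 weeks, or who discontinued any study intervention due to toxicity" before that period ended.

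Section 10.5.1.2 adds a DMC tolerability review of the first 8 participants randomized to Arm A: "This analysis will occur after the 8 participants have completed 6 weeks of treatment". It gives no event count and refers details to the DMC charter. Section 5.1.4 describes the charter's initial safety review differently: the first 12 randomized safety-evaluable participants, at 6 weeks of treatment.

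Other safeguards apply from the first dose:
- Safety Management Team (SMT) signal detection at least monthly, and ad hoc DMC review (Section 5.1.4).
- A sponsor commitment to pause enrollment and/or treatment if risk/benefit turns unfavorable (Section 3.3.3).
- Participant-level delay and discontinuation criteria (Table 7.4.2-1).

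**The concern.** Amendment 02 removed the safety lead-in. The evidence cited for tolerability at this dose is small: "no DLTs were reported in the 6 DLT-evaluable participants treated with BMS-986207 600 mg Q3W in combination with nivolumab plus ipilimumab". Zero of 6 has a one-sided 95% upper limit of 1 - 0.05^(1/6) = 39%. That limit concerns dose-limiting toxicities, not the 12-week Grade 3-4 TRAE rate, so it shows only how thin the evidence is.

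The sponsor chose a quantitative boundary as its formal monitor, yet the boundary is silent over the first stretch of dosing. The cause is the counting rule:
- A Grade 3-4 event in week 2, managed without stopping a drug, is already known and cannot be undone. It still does not enter the count until week 12.
- A participant who stops a drug for toxicity counts at once, while event-free participants wait 12 weeks. The early evaluable set is therefore enriched for events.

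So the boundary can be late when events are managed on treatment, and over-sensitive when events lead to discontinuation.

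**Working it through.** **Inputs.** Accrual, Section 10.2: "This assumes 12 months for accrual and a minimum of 10 months follow up". Size and allocation, Section 5.2: "Approximately 180 randomized participants are expected to be randomized in a 2:1 ratio to the 2 treatment arms". The boundary and evaluability rules are as above. Even accrual is an assumption; the protocol gives no ramp-up.

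**1. First row of the table.** With 5 events in 8, the posterior is Beta(0.66 + 5, 1.37 + 3) = Beta(5.66, 4.37), and Pr(rate > 40%) = 0.853. With 4 in 8 it is 0.651. The boundary is 5, as printed.

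**2. Arm A randomized when the boundary first applies.** Arm A is 180 x 2/3 = 120, or 10 per month, or 2.30 per week.
- Nobody evaluable early: 8 + 12 x 2.30 = 35.6, which is 30% of 120.
- At the 6-week DMC review: 8 + 6 x 2.30 = 21.8.
- Simulated, with early toxicity discontinuation spread evenly over 12 weeks: about 34 if 10% of participants stop, 33 if 18.1% stop (the CheckMate 227 figure in Section 3.3.3), and 31 if 30% stop. The 30% corresponds to half of events stopping a drug at a true event rate of 60% (0.5 x 0.60); the documents do not give it.
- Other accrual patterns, nobody evaluable early: linear ramp-up over 3 or 6 months gives 37.8 or 32.9; accrual over 14, 18 or 24 months gives 31.7, 26.4 or 21.8.

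**3. Effect of the counting rule on alarms.** The simulations use random accrual at 10 per month in Arm A, event times uniform over 12 weeks, the printed table from 8 to 60, and 2,000 to 3,000 trials per scenario. At a true rate of 33%, the written rule alarms in about 18% of trials if no event stops a drug and about 51% if half do.

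**4. Counting events as they occur, in treatment order, against the same table.** Median Arm A number randomized at the alarm, each count used alone:

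| True rate | Events that stop a drug | Written count | Treatment-order count |
|---|---|---|---|
| 60% | none | 38 | 28 |
| 60% | a quarter | 34 | 28 |
| 60% | half | 31 | 29 |
| 50% | half | 33 | 34 |
| 40% | half | 34 | 35 |

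The gain is about 10 participants where events are managed on treatment. It shrinks to 2 at a 60% rate when half of events stop a drug, and there is none at 40-50% in that case.

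The printed table matches its stated criterion at every size from 8 to 18. Above that, 24 entries are one event lower than the criterion gives. Row 8 is unaffected, and the simulations use the table as printed.

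**5. The first DMC review.** Twelve randomized at 2:1 gives 12 x 2/3 = 8 in Arm A, so Sections 5.1.4 and 10.5.1.2 may intend the same review. But Section 5.1.4 requires safety-evaluable participants, which under Section 10.3 generally means 12 weeks, and then sets the review at 6 weeks.

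**The case against.** The strongest reply is that early toxicity is far from unwatched. The SMT sees unblinded data at least monthly, can prompt an ad hoc DMC review, and the sponsor has committed to pause if risk/benefit becomes unfavorable. If 5 of the first 8 had events by week 6, the DMC would already be looking at them. Many Grade 3-4 events also require a drug to be stopped under Table 7.4.2-1, and those count at once. All of this stands, and it limits the point to the numeric boundary.

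Four stronger readings are tempting, and the documents do not support them:
- *That no toxicity rule applies to the first 31-36 Arm A participants.* Only the numeric aggregate boundary is missing.
- *That the 8-participant review has no criterion.* The protocol states none; the charter may, and it is not available.
- *That the difference in numbers randomized is a number of participants spared.* The boundary is non-binding and prompts a DMC contact; it does not itself stop randomization.
- *That treatment-order counting could replace the written rule at no cost.* It is a different rule. If half of events stop a drug, alarm probability falls from 51% to about 16-18% at a true rate of 33%, and from 98% to 90% at 50%.

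**Conclusion.** The point holds in a limited form. The protocol has no numeric aggregate boundary before 8 Arm A participants are safety-evaluable, states no threshold for the 6-week review, and leaves observed Grade 3-4 events uncounted until week 12 when the participant stays on all drugs.

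About 31-36 Arm A participants are randomized first. The upper figure needs even 12-month accrual; the lower also needs roughly 30% of participants to stop a drug early for toxicity. Across the accrual patterns tried, the range is about 22-38.

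The benefit of earlier counting depends on the share of events that stop a drug, which the documents do not give. It runs from about 10 fewer randomized at the alarm to none. This is a cheap improvement to an existing prompt, not a gap in overall safety oversight.

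**What to change.** In Section 10.5.1, keep the prior, the 40% limit, the 0.85 cut-off, the non-binding status and the written boundary. Add that the existing DMC contact is also made once the number of participants with an observed Grade 3-4 TRAE among the first m treated Arm A participants, in order of treatment, reaches the tabulated boundary for m. State in Section 10.5.1.2 that this includes m = 8 at the 6-week review.

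Because the written boundary stays, no existing alarm is lost, and contact is made at whichever count is reached first. The event enrichment in the written count remains, and the DMC should read an early crossing with that in mind.

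Reconcile Section 5.1.4, the definition in Section 10.3 and Section 10.5.1.2 on which participants trigger the first DMC review, and when.

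The cost is protocol and charter wording plus some additional ad hoc DMC reviews. One source is a participant who has an event and leaves treatment before week 12 for a reason other than toxicity: the treatment-order count includes that event, but the written count may never do so. No dose, treatment-stopping or enrollment-hold rule is proposed.
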